**Information on elective terminations, spontaneous abortions and stillbirths**

Information on elective TOPFA is not available from SWE, while in NOR information on pregnancy terminations is available only from GW 12 onwards. Furthermore, information on spontaneous abortions is incomplete in this study, as only women treated in hospitals due to spontaneous abortions are included in the data. Usually spontaneous abortions are in the early pregnancy and women may not even know yet about the pregnancy. Therefore estimates based on hospital records lead to underestimation of the actual number of spontaneous abortions. However, it is expected, but not certain, that the underestimation of spontaneous abortions would be comparable across cohorts. Therefore, any differences observed between cohorts are likely to be due to the differences in cohort exposure. As noted in section 9.7.2, the denominator for the prevalence of MCAs includes the number of elective terminations and the number of births (still or live). Because data on elective terminations are not available in SWE, the prevalence of MCAs will be calculated first in the data from FIN and NOR. The prevalence of MCAs will then be re-calculated to include MCAs identified from SWE. However, the denominator for this prevalence will exclude the elective TOPFAs identified from FIN and NOR.

Because information on elective pregnancy terminations is not available from SWE, analyses on MCAs will be calculated including TOPFA with Finnish and Norwegian data and for births without TOPFA including data from all three countries.

Information on pregnancy terminations is available from GW 12 onwards from the Norwegian data, and therefore, information on early pregnancy terminations conducted before GW 12 could result in incomplete data. Therefore we will conduct separate analyses by trimesters on pregnancy terminations.

Information on stillbirths is available from GW 28 onwards from the Swedish data. Country-specific prevalence rates will be estimated for outcomes, where stillbirths are included as nominator, or denominator.

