## 7 Rationale and background

MS is the most common chronic neurologic disability in young adult females of childbearing age (Baird & Dalton 2013). Women with MS are confronted with questions relating to pregnancy and pharmacological MS therapy. It is commonly understood that MS relapses are fewer during pregnancy, but also that medication taken before conception or in early pregnancy could negatively affect the outcome of the pregnancy. Experience with exposure to IFN- $\beta$  products during pregnancy has shown no clear association of adverse outcomes such as low birth weight (LBW), congenital anomaly or spontaneous abortion (Lu et al. 2012). However, it is contraindicated to initiate treatment with IFN- $\beta$  products during pregnancy. It is also recommended that if a woman becomes pregnant during treatment, she should be informed of the potential hazards and discontinuation of therapy should be considered. In patients with a high relapse rate before treatment start, the risk of a severe relapse following discontinuation of IFN- $\beta$  in the event of pregnancy should be weighed against a possible increased risk of spontaneous abortion. There are little data on newer MSDMD substances (e.g. fingolimod) (Lu et al. 2012).

This study addresses a request from the European Medicines Agency's CHMP to identify pregnancy outcomes in the MS population unexposed to IFN- $\beta$  products for comparison with the ongoing European IFN- $\beta$  Pregnancy Registry sponsored by the four European MAHs of IFN- $\beta$ s.

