### 9.7.8 Multiplicity adjustment

No formal adjustments for multiple comparisons will be performed. It should be noted that several comparisons will be made and some of the significant results may be due to chance although this is a population-based study which collects information from all MS pregnancies in FIN, SWE and NOR during the specified follow-up period.

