### **Information on MS disease**

It is known that there are regional and international differences in prevalence and incidence of MS. As for information on age at MS onset, disease status, and disease severity are not available from all MS data sources of these countries, the effect of MS and MSDMDs on these pregnancy outcomes in patients with different types of MS cannot be distinguished in this study. Therefore, confounding by indication is possible.

MS is more prevalent in Northern European countries than in southern part of Europe. It is unlikely that drug-related effects are due to the prevalence of the disease, but the large study population increases the likelihood of observed rare adverse outcomes. Information on country and region will be included in the descriptive, multivariate, as well as sensitivity analyses in this study.

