**Information on alcohol use and other abuse substances**

Information on maternal alcohol use or other substance abuse is not available in this study, but it is a potential confounding factor. Heavy alcohol use may affect the risk for spontaneous abortion, and also other pregnancy outcomes. However, it is not expected that the relative risks in relation to IFN- $\beta$  exposure would differ by substance abuse.

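### Section 9.9 reads any cohort difference in spontaneous abortion as likely due to exposure, but comparable under-recording would not rule out chance or confounding

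*Protocol*

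**What the plan says.** Objective 4 (Section 8) compares the prevalence of spontaneous abortion between cohorts 1 and 3, 1 and 4, and 2 and 3. It notes that only events requiring hospital treatment are available. Table 6 (Section 9.7.2) sets the denominator as all pregnancy events.

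Section 9.9, under the heading on elective terminations, spontaneous abortions and stillbirths, says that hospital records undercount these losses. It then says that "it is expected, but not certain, that the underestimation of spontaneous abortions would be comparable across cohorts". The next sentence draws the conclusion: "Therefore, any differences observed between cohorts are likely to be due to the differences in cohort exposure".

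Other parts of the protocol bear on the same comparison:

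- Section 9.9, on MS disease, after noting that severity is not available from all MS data sources: "Therefore, confounding by indication is possible".
- Section 9.9, on alcohol, which is not recorded and is called a potential confounder: "Heavy alcohol use may affect the risk for spontaneous abortion, and also other pregnancy outcomes".
- Section 9.7.8: "No formal adjustments for multiple comparisons will be performed", and "several comparisons will be made and some of the significant results may be due to chance".
- Section 9.9, on study power: the study is not powered for individual pregnancy outcomes.
- Section 9.3.2.2: spontaneous abortion diagnoses in the Patient Registers have had no specific validity study.

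**The concern.** The inference has one premise, equal under-recording, and a conclusion much wider than that premise supports. Equal recording answers one question: whether the exposed and unexposed cohorts lose cases at the same rate on the way into the register. It says nothing about whether the remaining difference is sampling error, or whether the women who used IFN-β differ in disease severity or other risk factors. The wording covers any observed difference and attaches no interval or other condition.

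The outcome matters. Section 7 says that, for some patients, the risk of relapse after stopping IFN-β "should be weighed against a possible increased risk of spontaneous abortion". An interpretation written in advance that favours exposure could turn bias or chance into a safety signal. It could equally turn a downward bias into reassurance.

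**Working it through.** **1. The protocol's own figure.** Section 9.5 gives a minimum detectable relative risk of 1.72 for the composite outcome, with 294 vs 1270 pregnancies, a baseline of 24/331 = 7.3%, 80% power and 5% two-sided alpha. The two-proportion normal approximation (pooled variance under the null, unpooled under the alternative) returns 1.72. No stated figure is in error. The protocol gives no such figure for spontaneous abortion.

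**2. Premise against conclusion.**

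| Explanation for a cohort difference | Addressed by equal under-recording? | Where the protocol admits it |
|---|---|---|
| Differential ascertainment | Yes, if the premise is true | 9.9, same paragraph (not certain) |
| Chance | No | 9.7.8 |
| Low power for single outcomes | No | 9.9, study power |
| Confounding by indication | No | 9.9, MS disease |
| Unmeasured alcohol use | No | 9.9, alcohol |

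Four of the five lines are untouched by the premise.

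**3. Precision for this outcome.** The recorded prevalence is not stated, so assume 5%, 10%, 15% or 20%. By the method of step 1, the minimum detectable relative risk for 294 vs 1270 is then 1.90, 1.59, 1.46 or 1.38.

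**4. Size of a recording bias.** Let s be the true share of pregnancies ending in spontaneous abortion and r the probability that such a loss is recorded. All other pregnancy events are taken as fully recorded. An unrecorded loss also drops out of the denominator of all pregnancy events, so the recorded prevalence is

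q = s·r / (1 − s + s·r).

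Assume s = 0.12 in both cohorts (no effect):

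- r = 0.50: 0.060 / 0.940 = 0.0638
- r = 0.60: 0.072 / 0.952 = 0.0756
- r = 0.70: 0.084 / 0.964 = 0.0871
- r = 0.75: 0.090 / 0.970 = 0.0928

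| Recording, unexposed vs exposed | Spurious RR | Recording ratio = odds ratio | p < 0.05 with 294 vs 1270 |
|---|---|---|---|
| 60% vs 70% | 0.0871 / 0.0756 = 1.15 | 1.17 | 11% |
| 60% vs 75% | 0.0928 / 0.0756 = 1.23 | 1.25 | 18% |
| 50% vs 70% | 0.0871 / 0.0638 = 1.37 | 1.40 | 31% |

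The last column is from 400,000 simulated pairs of binomials. With equal recording (60% in both) it is 5%.

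**5. Why the odds scale.** From the formula, q / (1 − q) = r · s / (1 − s). The observed odds ratio is therefore the true odds ratio times the recording ratio exactly. The relative risk moves by less than the recording ratio, so dividing it by that ratio would over-correct.

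**6. Size of a confounding bias.** Assume an unmeasured factor that doubles the risk, present in 40% of exposed and 20% of unexposed women. The spurious relative risk is (0.4·2 + 0.6) / (0.2·2 + 0.8) = 1.4 / 1.2 = 1.17, even with perfect recording.

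**The case against.** The best reply is that this is a remark in a limitations section, not an analysis rule. It says likely, and it follows an open admission that the premise is uncertain. In context it may mean no more than that under-recording is not expected to explain a difference. The Abstract plans adjusted log-binomial comparisons of the pregnancy outcomes with relative risks, 95% CIs and p-values, and Section 9.7.4 places spontaneous abortion among the outcomes compared. A report that follows the protocol would also carry the caveats on confounding, chance and power.

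Most of this stands. A reader might infer that the protocol has a mechanical rule attributing every difference to IFN-β without a test. The documents do not support that: the attribution is hedged and interval estimates are planned. Nor is it informative that two observed prevalences almost never coincide exactly when there is no effect. That is ordinary sampling error, and it is what the CI is for.

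A reader might also take Section 7 as showing that exposed women are more likely to be seen and coded for an early loss. Section 7 concerns informing women and weighing discontinuation. It says nothing about hospital attendance or coding, so unequal recording is a possibility and not a documented fact.

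The alcohol paragraph does offer a reassurance: relative risks are not expected to differ by substance abuse. That concerns effect modification and does not answer confounding.

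What the reply does not rescue is the inference itself. Hedged or not, it draws a causal reading from a premise about recording alone, in the same section that lists other explanations.

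**Conclusion.** The point holds as an unsupported causal inference that is inconsistent with the protocol's own limitations. It concerns the interpretation of a secondary objective. No estimate, cohort, model or table is affected.

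If recording differs as in the three assumed scenarios, a null effect would appear as a relative risk of about 1.15, 1.23 or 1.37. At the planned sizes, most such studies would still not reach p < 0.05 (11%, 18% and 31% would). These figures rest on an assumed 12% true loss, assumed recording probabilities and full recording of other pregnancy events. None of these values is in the protocol. The logical gap does not depend on them, because chance and confounding remain even when recording is equal.

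**What to change.** Delete the sentence in Section 9.9 and replace it with text along these lines:

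*The outcome is hospital-treated spontaneous abortion. Comparable under-recording across cohorts would limit differential ascertainment only. Differences between cohorts will be interpreted from the adjusted RR and its 95% CI. Chance, confounding by indication, unmeasured alcohol use and differential recording remain alternative explanations.*

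Add one reported quantity: the exposed/unexposed recording ratio that would move the estimate, and the CI limit nearer the null, to the null. Compute it on the odds scale (recorded losses relative to other pregnancy events). There the tipping ratio is simply the observed odds ratio, or its confidence limit. State that this takes other pregnancy events as equally recorded in both cohorts. No acceptance range for the ratio and no significance condition is needed.

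The cost is a text change, one extra line of calculation on data already assembled, and a weaker causal statement for this outcome.

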**Information on maternal age at LMP**

LMP is available from the registers if the pregnancy outcome is live birth, stillbirth or elective termination of pregnancy. If the pregnancy outcome is either spontaneous abortion or ectopic pregnancy, then the date of diagnosis but not the date of LMP will be available. In the latter two cases, in which maternal age is not available at LMP, the average time from LMP to the date of diagnosis will be subtracted from maternal age at diagnosis to approximate maternal age at LMP. For the average time from LMP to spontaneous abortion or to ectopic pregnancy, same estimates as in Nybo-Andersen et al 2000 will be used (spontaneous abortion: 9 and ectopic pregnancy: 8 weeks). These average estimates can be further justified based on previous studies and current care guidelines (spontaneous abortion: Cramer and Wise 2000, Tong et al 2008; ectopic pregnancy: Saxon et al 1997, Association of Finland Medical Society Working Group (2014) Current care guidelines, Ectopic pregnancies (in Finnish)).

**Information on alcohol use and other abuse substances**

Information on maternal alcohol use or other substance abuse is not available in this study, but it is a potential confounding factor. Heavy alcohol use may affect the risk for spontaneous abortion, and also other pregnancy outcomes. However, it is not expected that the relative risks in relation to IFN- $\beta$  exposure would differ by substance abuse.

**Information on pregnancy family history**

Information on family history on pregnancies is not available in MBRs. Therefore, for example, heredity in multiple pregnancies cannot be evaluated in this study.

### **Variation in follow-up period**

The follow-up periods vary between the three Nordic countries: In FIN the follow-up period for the registration of MCA is 12 months after birth, in SWE 6 months. In NOR malformations are registered in the MBR and the newborns are followed until the end of the stay at the birth clinic (usually at least 4 days). To address this, analyses will be done with stratification by country.

### **Relevance of results to the European IFN- $\beta$ Pregnancy Registry**

Results of this retrospective cohort study are not directly comparable with the information derived from the European IFN- $\beta$  Pregnancy Registry. Available information on disease severity and other confounding factors differs between the health registers and the European IFN- $\beta$  Pregnancy Registry and in some cases is missing, such that the rates cannot be adjusted to be comparable. In addition, the pregnancy cases included in the Nordic health registers are population-wide and are not based on a sample, whereas the European IFN- $\beta$  Pregnancy Registry is based on spontaneous reports.

Furthermore, study and exposure periods differ between the countries in this study and follow-up periods in the European IFN- $\beta$  Pregnancy Registry. Also, it is known that there are regional and international differences in MSDMD treatment practices, MSDMDs on market and prevalence of MS. With the available data in this study we aim to partially control for some of these variations by stratification and adjustment for country, hospital district, year of pregnancy outcome, maternal age at LMP, time since MS diagnosis and duration of IFN- $\beta$  treatment.

### **9.10 Other aspects**

Not applicable.

## **10 Protection of human subjects**

This is a fully register-based study and patients will not be contacted in any phase of the study. The study does not affect the treatment of the patients.

EPID Research will receive unidentifiable data including SIDs only. Patient data handled by the researchers do not include PINs or other identification numbers, which ensures the data protection of the patients. EPID Research employees have undertaken professional secrecy agreements. The study databases will further be constructed and data will be handled according to the national data protection requirements.

The protocol will be subjected to relevant ethical committees in each country for review and approval. Register notifications of the forming study registers will be sent to the relevant data protection offices in each country.

## **11 Management and reporting of adverse events/adverse reactions**

According to Good Pharmacovigilance Practice, non-interventional post-authorisation studies based on secondary use of data, such as this study, do not require reporting of suspected adverse reactions in the form of Individual Case Safety Reports. All reports of adverse events/reactions will be summarised in the final study report.

## 12 Plans for disseminating and communicating study results

The principal investigator together with the co-investigators will write a study report. This report will be delivered to the sponsors. After study report, the principal investigator and co-investigators with co-authors will prepare (a) scientific manuscript(s) for academic publication. The principal investigator will ensure that authorship for all publications complies with the criteria defined by the International Committee of Medical Journal Editors. Each author should have participated sufficiently in the work to take public responsibility for the content ([www.icmje.org/recommendations/browse/roles-and-responsibilities/defining-the-role-of-authors-and-contributors.html](http://www.icmje.org/recommendations/browse/roles-and-responsibilities/defining-the-role-of-authors-and-contributors.html)).

A summary of the main results of the study, whether positive or negative and including results from prematurely terminated studies, will always be made available to the public. The principal investigator and co-investigators will be responsible of publication of the results. An abstract of the study findings will be provided through the ENCePP e-register of studies within three months following the final study report. The principal investigator may ask the ENCePP Secretariat to delay the publication of this abstract for a limited period pending response to peer-review comments. In no way shall the interpretation and presentation of the results be aimed towards any commercial, financial or personal interests. The study Sponsors are entitled to view the final results and interpretations thereof at least 30 days prior to submission for publication and to comment in advance of submission and without unjustifiably delaying the publication.

The final study report may be used for the discussions with the competent authorities as required.

**Annex 1. List of stand-alone documents**

Number	Document reference number	Date	Title
1.	Feasibility study report	11 Dec 2013, Version 1.0	Pregnancy outcomes in an unexposed Multiple Sclerosis population in the Nordic countries

CONFIDENTIAL

## **Annex 2. ENCePP checklist for study protocols**

A copy of the ENCePP Checklist for Study protocols available at

[http://www.encepp.eu/standards\\_and\\_guidances/index.html](http://www.encepp.eu/standards_and_guidances/index.html) completed and signed by the main author of the study protocol should be included in Annex 2. The checklist will facilitate the review of the protocol and evaluation of whether investigators have considered important methodological aspects.

CONFIDENTIAL

### Annex 3. Potentially or clearly harmful drugs during pregnancy

Definitions for the risk categories in the Swedish Catalogue of Approved Drugs during pregnancy (FASS, 1993) classification system are given below. This classification comprises 4 separate categories (A, B, C, D): A includes the safest drugs; B is divided into 3 subgroups (B1, B2, B3); and C and D categories are used for drugs which may have different risks for the foetus depending on the evidence on which the risk is based.

Risk category	Description
A	
Medicinal products which may be assumed to have been used by a large number of pregnant women and women of child-bearing age without any identified disturbance in the reproductive process, e.g. an increased incidence of malformations or other direct or indirect effects on the foetus. This category comprises: drugs that have been available for many years; those that have been used by many pregnant women and women of child-bearing age and; drugs for which satisfactory retrospective studies in pregnant women are considered to have been carried out.

B	
Medicinal products which may be assumed to have been used only by a limited number of pregnant women and women of child-bearing age without any identified disturbance in the reproductive process having been noted so far, e.g. an increased incidence of malformations or other direct or indirect harmful effects on the foetus. As experience of effects of medicinal products in man is limited in this category, results of reproduction toxicity studies in animals are indicated by allocation to one of 3 subgroups B1, B2 or B3 according to the following definitions:
 
B1: Reproduction toxicity studies have not given evidence of an increased incidence of foetal damage or other deleterious effects on the reproductive process.
 
B2: Reproduction toxicity studies are inadequate or lacking, but available data do not indicate an increased incidence of foetal damage or other deleterious effects on the reproductive process.
 
B3: Reproduction toxicity studies in animals have revealed an increased incidence of foetal damage or other deleterious effects on the reproductive process, the significance of which is considered uncertain in humans.

C	
Medicinal products, which by their pharmacological effects have caused or must be suspected of causing, disturbances in the reproductive process that may involve risk to the foetus without being directly teratogenic. If experimental studies in animals have indicated an increased occurrence of foetal injuries or other disturbances of the reproductive process of uncertain insignificance in humans, these findings are to be stated for drugs in this category.

D	
Medicinal products, which have caused an increased incidence of foetal malformations or other permanent damage in humans or which, on the basis of e.g. reproduction toxicity studies, must be suspected of doing so. This category comprises drugs with primary teratogenic effects that may directly or indirectly have a harmful effect on the foetus.

[figure not shown]
In this study, the following drugs (ATC codes) from categories C and D will be included in this study as potentially teratogenic drugs or teratogenic drugs.

	ATC codes						
Potentially teratogenic drugs – risk category C	A01AB11	A01AC01	A02BC02	A03AB02	A03FA01	A04AA03	A04AD12
	A05AA02	A07DA03	A07EA02	A07EA06	A10BB01	A10BB07	A10BB12
	A10BG02	A10BG03	A10BH01	A10BX02	A10BX03	A11HA30	B01AC06
	B01AC11	B01AC30	B01AD02	B01AD07	B01AD11	B01AE07	B03XA01
	C01BC03	C01BC04	C01BD01	C01BD05	C01CA04	C01CX08	C01EA01
	C02AC05	C03AA03	C03BA11	C03CA01	C03EA01	C04AD03	C07AA03
	C07AA05	C07AA07	C07AB02	C07AB03	C07AB05	C07AB07	C07AB09
	C07AG01	C07AG02	C07FB02	C08CA01	C08CA02	C08CA03	C08CA05
	C08CA06	C08CA07	C08CA13	C08DA01	C08DB01	C08DB01	C10AA03
	C10AA04	C10AA07	C10AB02	C07AB09	C07AG01	C07AG02	C10AB04
	C10AB05	D01AA02	D01AC07	D01AC08	D01AE16	D05AX03	D05AX52
	D06BB03	D06BB04	D07AB01	D07AB02	D07AB08	D07AC01	D07AC03
	D07AC13	D07AD01	D07BC01	D07CC01	D07XC01	D08AG02	D10AD01
	D10AD03	D11AH01	D11AX01	D11AX18	G01AF08	G02AB01	G02BB01
	G02CB03	G03AA11	G03AA12	G03AA13	G03AB03	G03AB05	G03AB06
	G03AC01	G03AC03	G03AC08	G03AC09	G03CX01	G03DA02	G03FA01
	G03FA12	G03FA17	G03FB05	G03FB06	G03GA01	G03AA07	G03AA09
	G03AA10	G03GA01	G03GB02	G03HB01	H01CA02	H01CB02	H01CB03
	H01CC02	H02AA02	H02AB01	H02AB02	H02AB04	H02AB06	H02AB07
	H02AB08	H03BB01	H05AA02	J01CA08	J01EA01	J01EE01	J01EE02
	J01FA09	J01FA15	J01GB01	J01MA01	J01MA02	J01MA06	J01MA12
	J01MA14	J01XC01	J01XE01	J01XX08	J02AB02	J02AC01	J02AC02
	J02AC03	J02AX04	J04AB02	J04AB04	J05AB01	J05AB11	J05AE02
	J05AE03	J05AE07	J05AF01	J05AF05	J05AF06	J05AF08	J05AR01
	J07BA02	J07BK01	L01XE01	L01XE06	L01XX19	L01XX23	L02AB01
	L02AE01	L02AE02	L02AE03	L02AE04	L02BA02	L02BG03	L02BG04
	L02BG06	L03AA02	L03AA10	L03AA13	L03AB05	L03AB10	L03AB11
	L04AA10	L04AB02	L04AB04	L04AD02	M01AB01	M01AB05	M01AB08
	M01AB15	M01AB51	M01AB55	M01AC06	M01AE01	M01AE02	M01AE03
	M01AE51	M01AG01	M01AH01	M01AH04	M01AH05	M01AX01	M01CB03
	M01CB03	M02AA07	M02AA10	M02AA15	M02AC	M03AB01	M03AX01
	M03BX02	M05BA03	M05BA04	M05BA06	M05BA07	M05BA08	M05BC01
N01AB07	N01AH01	N01AH02	N01AH06	N01AX01	N01AX10	N01BB10	
N01BB58	N02AA01	N02AA05	N02AA59	N02AB03	N02AE01	N02AX02	

	N02BA01	N02BA51	N02BG08	N02CA01	N02CA52	N02CC07	N03AE01
	N03AG06	N03AX09	N03AX11	N03AX12	N03AX14	N03AX15	N03AX16
	N05AA01	N05AB02	N05AB03	N05AB04	N05AD01	N05AD03	N05AE03
	N05AE04	N05AF01	N05AF03	N05AF05	N05AH03	N05AX08	N05AX12
	N05BA01	N05BA02	N05BA04	N05BA06	N05BA09	N05BA12	N05BB01
	N05CD02	N05CD05	N05CD07	N05CD08	N05CF01	N05CF02	N05CF03
	N06AA04	N06AA06	N06AA09	N06AA10	N06AA12	N06AB03	N06AB04
	N06AB05	N06AB06	N06AB10	N06AX03	N06AX05	N06AX11	N06AX16
	N06AX18	N06AX21	N06BA04	N06CA01	N06DA03	N06DA04	N06DX01
	N07AA02	N07AA51	N07AX01	N07BA01	N07BB04	N07BC02	N07XX02
	P01BA01	P01BA02	P01BB51	P01BC02	P02CA01	R01AC02	R01AC03
	R01AD01	R01AD08	R01AD09	R01AD11	R01AD12	R03AC13	R03AK06
	R03AK07	R03BA01	R03BA05	R03BB04	R05	R05DA20	R06A
	S01AD03	S01AX11	S01AX19	S01BA01	S01BA13	S01BC03	S01EC01
	S01ED51	S01EE01	S01EE03	S01EE04	S01GX06	S01JA01	S01LA04
	ATC codes						
Teratogenic drugs – risk category D	A02BB01	A16AX03	B01AA03	C01BA01	C02KX01	C09AA01	C09AA02
	C09AA03	C09AA04	C09AA05	C09AA06	C09BA02	C09BA03	C09BA05
	C09BA06	C09BA15	C09CA01	C09CA02	C09CA03	C09CA06	C09CA07
	C09CA08	C09DA01	C09DA02	C09DA03	C09DA06	C09DA07	C09DB01
	C10AA01	C10AA02	C10AA05	D05BB02	D06AX04	D10AD04	D10BA01
	D11AX10	G03BA03	G03DC02	G03DC03	G03FA14	G03FB08	G03GA06
	G03HA01	G03XB01	G03XC01	G04CB01	L01BC02	L01BC05	L01BC06
	L01CA04	L01CB01	L01CD01	L01CD02	L01DB01	L01DB03	L01DB06
	L01DC01	L01DC03	L01XA01	L01XA02	L01XC07	L01XX05	L01XX11
	L01XX14	L01XX17	L01XX32	L02BA01	L02BA03	L02BB03	L03AB07
	L03AB08	L04AA13	L04AX01	L04AX02	L04AX03	N03AB02	N03AB05
	N03AF01	N03AF02	N03AG01	N03AG04	N05AN01		

